5.2 Treatment Protocol

- Topical lidocaine 5% pre-treatment
- Total 0.5cc Gardasil 9 distributed across 3-5 index warts
- Intradermal injection immediately subjacent to keratotic wart body

6. Safety Monitoring

6.1 Adverse Event Monitoring

- Weekly phone follow-up after injections
- Documentation of local and systemic reactions
- Access to study clinicians for concerns
- Monthly research team meetings to review safety

6.2 Stopping Criteria

- Intolerable adverse effects
- Worsening of condylomata

- Pregnancy

7. Statistical Analysis Plan

7.1 Sample Size

Pilot study of 10 participants; no formal sample size calculation as effect size is unknown.

7.2 Analysis Populations

- Intent-to-treat (ITT): All participants receiving ≥ 1 dose
- Per-protocol: Participants completing study without major protocol deviations

7.3 Primary Endpoint Analysis

Paired t-tests comparing baseline to week 12:

- Wart number
- Mean wart size
- Total skin area covered by warts

Significance level: $\alpha = 0.05$

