2.1 Primary Objective

To assess the efficacy of intralesional Gardasil 9 in treating genital condylomata through:

- Reduction in wart number
- Reduction in mean wart size
- Reduction in total skin area covered by warts

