2.2 Secondary Objectives

- Evaluate patient-centered outcomes using:
 - CECA (Specific Questionnaire for Condylomata Acuminata)
 - Dermatology Quality of Life Index (DLQI)
 - Global patient satisfaction (1-5 scale)
- Assess tolerability of intralesional Gardasil 9

3. Study Design

- Prospective, open-label, single-arm proof-of-concept study
- Duration: 12 weeks per participant
- Sample size: 10 participants
- Two treatment visits (Week 0 and Week 4)

4. Study Population

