4.1 Inclusion Criteria

- Age \geq 18 years
- Signed informed consent
- Minimum of 3 genital condylomata, each >3 mm in size

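### Do three unranked primary endpoints, each tested at 0.05 in a 10-person pilot, need a multiplicity rule?

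*Combined protocol and SAP*

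**What the plan says.** Section 2.1 sets one objective, "To assess the efficacy of intralesional Gardasil 9 in treating genital condylomata through" three reductions: in the count of warts, in their average size and in the area they cover. Section 7.3 gives each measure the same treatment, "Paired t-tests comparing baseline to week 12", and closes with "Significance level: $\alpha = 0.05". No section orders the three measures, requires one or all of them to succeed, adjusts for three tests, calls the p-values exploratory, or says whether the tests are one- or two-sided.

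The setting is also stated. Section 3 describes a "Prospective, open-label, single-arm proof-of-concept study", and section 7.1 says "Pilot study of 10 participants; no formal sample size calculation as effect size is unknown". The stopping criteria in section 6.2 do not refer to any test result, and no later decision in the document is tied to significance.

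**The concern.** One efficacy objective with three tests at 0.05 is a familiar multiplicity problem. If whichever endpoint turns out significant is presented as the efficacy result, the stated 0.05 no longer describes the error rate of that conclusion, and the plan does not rule this reading out.

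The measures can also disagree. Section 4.1 requires a "Minimum of 3 genital condylomata, each >3 mm in size". Take a participant with circular warts of 4, 4, 4 and 8 mm whose three small warts clear. The count and the area fall. The mean size rises if it is taken over the remaining wart only, but falls if cleared warts count as 0. With no success rule, the reading of mixed results would be settled after the data are seen.

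**Working it through.** **Inputs.** Three primary endpoints (2.1, 7.3); one level of 0.05 (7.3); 10 participants (3, 7.1), so 9 degrees of freedom per test with complete data. The plan does not give sidedness or the correlations between endpoints. Two-sided tests are assumed, which puts 0.025 in the improvement direction for each test, and the correlation is varied. The plan derives no power or overall error rate, so it has no figure of its own to reproduce.

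**Any-one rule, no true change.**
- Independent endpoints: 1 − 0.975³ = 1 − 0.9269 = 0.0731, or 7.3%.
- Upper bound for any correlation: 3 × 0.025 = 7.5%.
- Equal correlations, from 400,000 simulated trials with n = 10 and normal changes:

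| Correlation | Any one improves | All three improve |
|---|---|---|
| 0 | 7.3% | 0.0% |
| 0.3 | 6.9% | 0.0% |
| 0.5 | 6.5% | 0.1% |
| 0.7 | 5.7% | 0.4% |
| 0.9 | 4.4% | 1.0% |
| 0.95 | 3.8% | 1.4% |

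A single test in the same simulation gave 2.5%, as it should. Requiring all three keeps the error below 2.5% throughout.

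**Area tied to number and size.** Total area depends on the other two measures, so full independence is not a realistic case. With area as the sum of number and size on a log scale, and a number-size correlation from −0.3 to 0.7, the any-one error runs from 6.5% down to 4.5%. With area as a product on the natural scale (assumed 3-14 warts, 10-40% within-person variation), it is 3.8% to 5.8%. The excess over 2.5% is therefore between 3.8 − 2.5 = 1.3 and 6.5 − 2.5 = 4.0 percentage points. In the second model the test on area alone gave 1.1-2.2%, so 2.5% is itself a normal-theory comparator.

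**If the tests were one-sided at 0.05.** The comparator would be 5%, and the any-one error under independence 1 − 0.95³ = 14.3%.

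**Price of a correction.** At an assumed standardised change of 1.0 on all three endpoints, an unadjusted test has 80% power. Holm at a family-wise two-sided 0.05 gives 73%, 71% and 68% per endpoint at correlation 0, 0.5 and 0.9. The chance of at least one significant endpoint falls from 99% to 94% at correlation 0, and from 88% to 72% at 0.9.

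**Does disagreement come from the missing success rule?** In the four-wart example:
- Count: 4 to 1.
- Area: π/4 × (3 × 16 + 64) = 88.0 mm² to π/4 × 64 = 50.3 mm².
- Mean size at baseline: 20/4 = 5 mm. Over remaining warts it becomes 8/1 = 8 mm; with cleared warts scored 0 it becomes 8/4 = 2 mm.

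Under the second convention all three measures improve and no success rule is needed. The conflict comes from how mean size is defined.

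Wart-level simulation, with an assumed 50% clearance regardless of size, shows the same. With cleared warts scored 0, the all-three rule succeeds in 97-99% of trials when survivors do not shrink. With remaining warts only, it succeeds in about 2% when survivors do not shrink, 46-55% with an assumed 10% mean shrinkage, and 80-86% with 20%. The 2% is simply the false-positive rate of an endpoint on which that scenario assumes no effect.

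**The case for a change.** The best argument for amending the plan is that it chose to set a threshold and to speak of efficacy, and section 10 schedules a manuscript. A plan that sets a threshold should say what crossing it means. One sentence would do it, with no new data, visits or participants, and calling the p-values nominal costs no power.

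It stands that the rule is unstated, that the any-one error exceeds 2.5% under every correlation tried, and that the handling of cleared warts should be settled before analysis. So should the question whether all warts or only those that received vaccine (the dose is "distributed across 3-5 index warts") are measured. Those last two are endpoint definitions, separate from multiplicity.

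It does not follow that the plan must change. The inflation arises only under a reading that the plan never adopts. Naming one primary endpoint would mean preferring one of the sponsor's three measures and moving the others into sections 2.2 and 7.4. Holm gives up power in a sample of 10. Reasonable statisticians would differ on both. The nominal label does no more than write down what the design already implies.

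**Conclusion.** The concern does not call for a change. The omission is real but is of the kind an analyst fills sensibly: report all three changes from baseline to week 12, treat the p-values as nominal, and rest no efficacy claim on one of them.

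Under the least favourable reading, false improvement rises from 2.5% to about 4-6.5%, or at most 7.3% under independence; under an all-three reading it does not rise. These sizes assume two-sided tests, normal changes, complete data and no true change, with correlations the plan does not supply.

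The practical weight is small because the null hypothesis is no mean change from baseline. With no control arm, rejecting it cannot separate a vaccine effect from improvement without treatment, and no multiplicity rule alters that.

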7.4 Secondary Endpoint Analysis

- Paired t-tests comparing baseline to week 12:
 - DLQI scores
 - CECA scores
- Descriptive statistics for:
 - Global satisfaction scores
 - Adverse events
 - Treatment tolerability

7.5 Missing Data

- Last observation carried forward for early discontinuation
- Sensitivity analyses excluding missing data

8. Data Management

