5.1 Visit Schedule

Visit 1 (Week 0)

1. Informed consent
2. Baseline data collection:
 - Demographics
 - Medical history
 - Medication review
 - Condylomata history
3. Pregnancy test if applicable
4. Photography and measurements
5. Questionnaires (CECA, DLQI)
6. Shave biopsy ($\leq 5 \times 5 \text{ mm}$) for histologic confirmation
7. First Gardasil 9 injection
8. 15-minute observation period

Phone Follow-up 1 (Week 1)

- Assess adverse effects
- Arrange follow-up if needed

Visit 2 (Week 4)

1. Assessment of treatment response
2. Photography and measurements
3. Questionnaires (CECA, DLQI)
4. Second Gardasil 9 injection if indicated

5. 15-minute observation period

Phone Follow-up 2 (Week 5)

- Assess adverse effects
- Arrange follow-up if needed

Visit 3 (Week 12)

1. Final assessment
2. Photography and measurements
3. Questionnaires (CECA, DLQI, satisfaction)

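### With any early dropout, carrying forward the Week 4 or baseline value biases the Week 12 change in an unknown direction and leaves its precision unreliable; the planned complete-case check helps only in part

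*Combined protocol and SAP*

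**What the plan says.** Section 7.5 has two rules. The main one is "Last observation carried forward for early discontinuation"; the other is "Sensitivity analyses excluding missing data", which I read as a complete-case analysis. Section 7.3 then specifies "Paired t-tests comparing baseline to week 12" for wart number, mean size and total area, and 7.4 does the same for DLQI and CECA. Neither section says how a filled value is treated in the test.

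Section 7.2 defines the ITT set as "All participants receiving" at least one dose. It does not say which analysis set is primary.

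Section 5.1 schedules measurements and questionnaires at Weeks 0, 4 and 12. At Visit 2, measurement is item 2 and item 4 is "Second Gardasil 9 injection if indicated". Section 6.2 lists worsening of the warts and intolerable adverse effects among the reasons for stopping.

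The study design section gives "Sample size: 10 participants", and 7.1 explains that no calculation was done because the effect size is unknown. No dropout rate is given, and no assumption is offered in support of carrying values forward.

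**The concern.** Only two readings can stand in for a missing Week 12 value. One is Week 4, which on the listed order precedes any second injection. The other is baseline, which scores an ITT participant who leaves before Week 4 as exactly zero change. Either is a fair substitute only if, among those who leave, wart status does not change on average after that reading. A design that offers a second dose at Week 4 and places its endpoint 8 weeks later gives no support for that.

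The main product of this study is an estimate of an unknown effect. With 10 participants, each departure is 10% of the data, so the missing-data rule can move the estimate visibly. The Week 4 wart, CECA and DLQI values are collected at a scheduled visit, yet 7.3 to 7.5 give them no analytic use beyond this fill.

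**Working it through.** **No plan figure to reproduce.** The documents give n = 10 and alpha 0.05, but no effect size, SD or dropout rate. The inputs below are assumptions chosen for illustration: mean reduction 30 points at Week 4 and 60 at Week 12, SDs 25 and 30, correlation 0.6.

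**1. Bias of the carried value.** With m of n participants lost,

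bias = (m/n) × (mean change at the carried reading − mean change at Week 12), both means taken among those lost.

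- Two lost at random after Week 4: 0.2 × (30 − 60) = -6 points, or 10% of the effect.
- Three lost at random after Week 4: 0.3 × (30 − 60) = -9.
- Two lost at random before Week 4: 0.2 × (0 − 60) = -12. Each such loss removes 10% of the effect.
- Partial reversal (60 at Week 4, 40 at Week 12), two lost at random after Week 4: 0.2 × (60 − 40) = +4, an overstatement.

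Simulation agrees. If loss depends on Week 4 response, the reversal case ranges from about +2 to +6.

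**2. Loss that depends on Week 4 response.** The two largest of ten standard normal values average about 1.27. If the two best Week 4 responders leave, their mean change is 30 + 25 × 1.27 = 61.8 at Week 4 and 60 + 0.6 × 30 × 1.27 = 82.9 at Week 12. The LOCF bias is 0.2 × (61.8 − 82.9) = -4.2. Simulated 95% interval coverage is about 90%.

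**3. The planned complete-case check.** Under random loss it is unbiased, with coverage about 95%. If the two best Week 4 responders leave, the eight who remain are off by -(2 × 1.27/8) × 0.6 × 30 = -5.7 points. If the two worst leave, the error is +5.7. Simulated coverage is about 91% in both cases.

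**4. Precision.** With two lost at random after Week 4, the true sampling variance of the LOCF mean is (8 × 30² + 2 × 25²)/10² = 84.5. The t-test's expected variance also picks up the spread between filled and observed means:

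[0.8 × 900 + 0.2 × 625 + (2 × 8)/(10 × 9) × 30²]/10 = (845 + 160)/10 = 100.5.

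The ratio of standard errors is √(100.5/84.5) = 1.09, so here the stated error is too large, not too small. Simulated mean widths of the 95% interval:

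| Case | Width |
|---|---|
| All ten observed | 41.7 |
| LOCF, two lost at random after Week 4 | 44 |
| LOCF, two lost at random before Week 4 | 52 |
| LOCF, two worst Week 4 responders lost | 54 |
| Complete case, two lost at random | 48.4 |

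The standard error was too small when the better responders left (ratio 0.89) and, under reversal, when the worse responders left (0.92). In the random-loss case, coverage of the true Week 12 change was 93%, but coverage around LOCF's own mean was 96.6%. The shortfall is therefore due to bias.

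**5. Using Week 4 in a likelihood estimate.** A regression of Week 12 change on Week 4 change, applied to the same post-Week 4 losses, had bias of at most about 0.2 points in a re-run of 8,000 simulations. Loss in these runs was random or depended only on Week 4, so missing-at-random held by construction.

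**The case against.** A reader might infer that single imputation makes the intervals too narrow and the p-values too optimistic. The documents and the arithmetic do not support that as a general statement. The plan specifies tests, not intervals. The direction of the precision error changes with who leaves: in the example the LOCF interval is often wider than its sampling error requires. In a separate simulation with no mean change at either follow-up visit, LOCF rejected in 4.3% to 5.0% of runs. What stands is that precision is unreliable and that under-coverage comes mainly from bias.

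It is also fair to say that 7.5 is not LOCF alone. The complete-case analysis is a real safeguard under random loss. It is not one when leaving depends on response, and 6.2 makes worsening a reason to stop, so that pattern is plausible.

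Three further points stand. Every magnitude here is assumed, and with no dropout nothing changes. The likelihood approach does not cure loss driven by events after Week 4 that were never measured, and that case was not simulated. The full three-visit model was not itself fitted; the comparison used its regression equivalent on change scores. Finally, this is a small open-label pilot, which limits the weight any one analysis choice should carry.

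**Conclusion.** The concern holds as a matter of bias. Any dropout mixes readings from before the second injection, or zero-change readings, into the Week 12 estimate, and the plan states no assumption that would make this harmless. The direction cannot be known in advance. In the assumed example the size is about -6 points for two lost at random after Week 4, about -12 for two lost at random before Week 4, and +2 to +6 for two lost after Week 4 if response partly reverses. These figures rest on the assumed means, SDs, correlation and number lost. That the t-test treats filled values as observed is the natural reading of 7.3, which is silent on it. The complete-case check mitigates only in part. This is worth changing before analysis because the change is cheap; it does not invalidate the study.

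**What to change.** In 7.5, make the main analysis a repeated-measures likelihood model on all observed Week 0, 4 and 12 values: visit as a factor, unstructured covariance, REML, Kenward-Roger degrees of freedom. Report the Week 12 minus baseline contrast for the three wart endpoints, CECA and DLQI. Keep LOCF and the complete-case analysis as sensitivity analyses.

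With complete data the unstructured model estimates the sample covariance, so the contrast has variance s²/10 (s being the SD of the change) on 9 degrees of freedom. That is the paired t-test of 7.3. If the model does not converge, fall back to the complete-case paired t-test. Compound symmetry is not a suitable fallback: it pools error across visits (18 degrees of freedom rather than 9 with complete data) and does not reproduce the planned test.

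The cost is SAP wording and a few lines of code, with no new data. The price is reliance on missing-at-random and sometimes a wider interval: about 51 points against 44 for LOCF with two lost at random after Week 4 in the example.

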1.1 Background

Genital warts (condyloma) affect 100-200 per 100,000 adults annually. While 90% are caused by HPV types 6 and 11, high-risk HPV types can co-occur and increase dysplasia/carcinoma risk. Current treatments have significant limitations: imiquimod shows variable efficacy (28-56%), while electrocautery, despite high clearance rates (94%), causes discomfort and scarring.

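### For participants who leave because their warts worsen, the one named sensitivity analysis deletes them, and LOCF shows the worsening only if it was measured before exit

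*Combined protocol and SAP*

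**What the plan says.** - Section 6.2 lists "Worsening of condylomata" among the stopping criteria. Neither it nor any other section says whether stopping ends treatment only or follow-up as well.
- Section 7.2 defines ITT as everyone who received at least one dose. The other set is "Per-protocol: Participants completing study without major protocol deviations".
- Section 7.3 tests wart number, mean wart size and total area with "Paired t-tests comparing baseline to week 12", at a significance level of 0.05.
- Section 7.5 is the whole missing-data plan: "Last observation carried forward for early discontinuation" and "Sensitivity analyses excluding missing data".
- Section 5.1 schedules photography and measurement at Weeks 0, 4 and 12. The Week 1 and Week 5 contacts are phone calls, with further follow-up arranged only if needed. No measurement at discontinuation is required. At Week 4 the measurements are listed before "Second Gardasil 9 injection if indicated".
- Section 3 sets two treatment visits (Weeks 0 and 4) and 10 participants in a single open-label arm.

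**The concern.** Stopping can depend directly on the outcome being tested. If a participant who worsens also leaves, the Week 12 value is missing because of how that participant was doing. The complete-case analysis and the per-protocol set then drop the same person, so the second is not an independent check on the first.

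What LOCF does depends on when the participant leaves:
- At Week 4, with the worsening measured there: the worsened value is carried, and LOCF is about neutral.
- Before Week 4: baseline is carried, which counts as no change.
- Between Weeks 4 and 12: the Week 4 value is carried, and it may precede or understate the worsening.

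In the last two cases LOCF and complete-case can err in the same direction, and nothing in section 7.5 would reveal it. With ten participants and no control arm, one or two such leavers can decide whether a section 7.3 test falls below 0.05.

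**Working it through.** The plan gives no effect, SD or dropout rate (section 7.1 says the effect size is unknown), so there is no figure to reproduce. From the documents: n=10, paired t-test, significance level 0.05. Sidedness is not stated, so two-sided is assumed. All other inputs are assumptions, on the scale of change in wart number.

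**Set-up.** There are k leavers, all with change x, and n1 = 10 - k completers with mean change m and SD s. The paired t-test is a one-sample t-test on the ten changes:
- Mean M = (n1·m + k·x)/10
- SS = (n1 - 1)s² + n1(m - M)² + k(x - M)²
- t = M / (√(SS/9)/√10), with 9 df

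**Two leavers, m = -3, s = 3, true leaver change +3.**
- All ten observed: M = (8×(-3) + 2×3)/10 = -1.8; SS = 63 + 11.52 + 46.08 = 120.6; t = -1.8/(3.66/√10) = -1.555; p=0.154.
- Complete-case (n=8): t = -3/(3/√8) = -2.828, 7 df; p=0.025.
- LOCF of baseline (x=0): M = -2.4; SS = 63 + 2.88 + 11.52 = 77.4; t = -2.588; p=0.029.

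| Analysis, two leavers truly at +3 | Mean change | p | Overstated reduction (warts) |
|---|---|---|---|
| All ten observed | -1.8 | 0.154 | 0 |
| LOCF, worsening (+3) measured at Week 4 | -1.8 | 0.154 | 0 |
| LOCF, baseline carried | -2.4 | 0.029 | 2×(3-0)/10 = 0.6 |
| LOCF, Week 4 value of -2 carried | -2.8 | 0.009 | 2×(3+2)/10 = 1.0 |
| Complete-case | -3.0 | 0.025 | 2×(3+3)/10 = 1.2 |

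With one leaver at +3, all-observed gives -2.4 (p=0.053) and complete-case (n=9) gives -3.0 (p=0.017).

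**Mean and p-value behave differently.** Dropping leavers who did worse than completers always moves the mean towards efficacy, but it also loses sample size. Two leavers at -2 did worse than completers at -3, yet all ten give p=0.009 against 0.025 complete-case. With one leaver at -2 it is 0.0105 against 0.0171. In this example complete-case gives the smaller p only when the leavers' change is above about -0.2 wart (two leavers) or -0.3 (one leaver), that is, about no change or worse.

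**Tipping point.** The leaver worsening at which the ten-participant p reaches 0.05, as a multiple of the completers' mean reduction:

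| Completer mean/SD | 1 leaver | 2 leavers |
|---|---|---|
| 1 | 0.95 | 0.29 |
| 1.5 | 1.60 | 0.69 |
| 2 | 1.81 | 0.83 |

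At a ratio of 0.8 with two leavers, complete-case is already p=0.058, so nothing tips.

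**Simulation with no true effect.** In 100,000 trials of 10, with Week 4 to Week 12 correlation 0.5 or 0.8, a participant leaves if the Week 4 change is in the worst 10% or 20%. The nominal chance of a false significant improvement is 0.025.
- Complete-case: 0.044 to 0.108
- LOCF of baseline (worsening never measured): 0.043 to 0.101
- LOCF of the measured Week 4 value: 0.010 to 0.023

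**The case against.** The strongest reply is that ITT with LOCF already covers the most likely case. Only two treatment visits exist, so after the Week 4 injection no scheduled treatment remains to stop. The stopping rule therefore acts mainly at Week 4, where warts are measured before any injection. A worsening found there enters the Week 12 test, and LOCF (p=0.154) then disagrees visibly with complete-case (p=0.025), so the planned pair would flag the problem. This stands. A reader might infer that no planned analysis can ever reflect an unfavourable outcome; sections 5.1, 7.2 and 7.5 together do not support that.

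A reader might also infer that dropping worse-off participants always makes the test look better. That is true of the mean change, not of the p-value, as shown above. Nor do the documents say that participants who stop must leave the study; that step is a condition of the point.

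It is also fair to say that the harmful case needs exit from follow-up together with unmeasured worsening, that the numbers rest on assumptions, and that in a ten-person proof-of-concept study individual results can simply be listed. These limit the weight of the point. They do not remove it: section 7.5 leaves follow-up after stopping open, requires no measurement at exit, and names as its only check an analysis that deletes the participants in question.

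**Conclusion.** The point holds in a conditional form. If a participant leaves for worsening, the named sensitivity analysis and the per-protocol set both drop that participant, and the mean change moves towards efficacy when leavers did worse than completers. The p-value falls only when leavers had about no change or worsened. LOCF is about neutral if the worsening was measured at Week 4, and too favourable if the carried value precedes or understates it. In that second case agreement between LOCF and complete-case is not evidence of robustness: with baseline carried, the example gives p=0.029 and p=0.025, against p=0.154 if all ten were observed.

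The size for this trial cannot be estimated. The illustrated overstatement of 0.6 to 1.2 warts rests on two leavers truly at +3 and completers at -3 with SD 3. With a stronger effect and a single leaver, the conclusion changes only if that leaver worsens by 1.60 to 1.81 times the completers' mean reduction. This is a worthwhile, cheap improvement, not a fatal flaw.

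**What to change.** 1. In sections 5.1 and 7.5, state that every dosed participant, including those who stopped, is photographed and measured at the scheduled Week 12 visit where possible, and that the observed value is used in ITT. State whether stopping under section 6.2 ends follow-up. Record the reason for stopping and any other wart treatment, with its date.
2. In section 7.5, add one ITT sensitivity analysis for each section 7.3 outcome. It applies to participants whose Week 12 value is missing after leaving for worsening, or was measured after other wart treatment. Assign the larger of baseline and the last value observed before such treatment, then increasingly worse values until the conclusion changes. Report this beside LOCF and complete-case, as scenarios and not bounds.

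The other-treatment field is needed because observed values alone can mislead. Section 1.1 notes "electrocautery, despite high clearance rates (94%), causes discomfort and scarring". If both leavers in the example (assumed baseline 6 warts) were cleared elsewhere, their change would be -6 and the observed mean (8×(-3) + 2×(-6))/10 = -3.6 (p=0.004), against -1.8.

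The first scenario is imperfect. It is still 0.6 wart too favourable if worsening to +3 was never measured (p=0.029 against 0.154), which is why the tipping-point step is needed. It is 2×(5-3)/10 = 0.4 wart too unfavourable if a Week 4 value of +5 later falls to +3.

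The cost is modest effort to bring stopped participants to an existing visit, two data fields, one more analysis per outcome, and a possibly less favourable result. The stopping criteria do not change.
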